### 1.2.7 Vaccination with Peptides or Peptide-Pulsed Dendritic Cells

There are limited studies that address the most effective means for induction of cytotoxic T cell responses in patients with cancer. Slingluff compared the use of peptide in adjuvant with peptides pulsed on dendritic cells in a small study in patients with melanoma. This study

**COMPARISON OF DENDRITIC CELLS VS. MONOCYTES AS STIMULATORS IN A MIXED LYMPHOCYTE REACTION MLR PULSED W/ TRITIATED THYMIDINE ON DAY 7**

showed a superior response with peptides in adjuvant compared with peptides pulsed on dendritic cells. T cell response was monitored in peripheral blood and draining lymph nodes. In patients vaccinated with peptide in adjuvant T cell responses were seen in 42% of peripheral blood samples and 80% of lymph nodes whereas in patients vaccinated with peptides pulsed on dendritic cells 11% showed response in the blood and 13% in the nodes. Despite the disparity in immunologic response rates objective responses were observed in both arms of the study. This study used immature dendritic cells and previous studies have shown that immature dendritic cells are ineffective in producing a cytolytic T cell response compared with mature dendritic cells. Another possible disadvantage with immature dendritic cells is their ability to induce tolerance. This study will address in a randomized fashion the immunogenicity of TARP peptides in adjuvant compared with TARP peptides pulsed on mature dendritic cells.

## **2 ELIGIBILITY ASSESSMENT AND ENROLLMENT**

### **2.1 ELIGIBILITY CRITERIA**

#### **2.1.1 Inclusion Criteria**

- 2.1.1.1 Males  $\geq$  18 years of age with histologically confirmed adenocarcinoma of the prostate.
- 2.1.1.2 HLA-A\*201 positive
- 2.1.1.3 Patients must have
  - 2.1.1.3.1 Completed and recovered from all prior definitive therapy (surgery, brachytherapy, cryotherapy or radiotherapy) for the primary tumor, or other definitive-intent local therapy.
  - 2.1.1.3.2 Stage D0 disease with documented biochemical progression documented by a rising PSA.
  - 2.1.1.3.3 No evidence of metastatic disease by physical examination, CT scan or bone scan.
  - 2.1.1.3.4 For patients following definitive radiation therapy or cryotherapy: a rise in PSA of  $>2$  ng/mL above the nadir (per RTOG-ASTRO consensus criteria).
  - 2.1.1.3.5 For patients following radical prostatectomy: 2 absolute PSA values  $> 0.3$  ng/mL (per NCCN guidelines)
  - 2.1.1.3.6 Non-castrate level of testosterone:  $\geq 50$  ng/dL (prior ADT allowed; must be  $\geq 6$  months since last dose of ADT).
  - 2.1.1.3.7 A Pre-Enrollment/Baseline PSADT  $> 3$  months and  $\leq 15$  months
    - 2.1.1.3.7.1 Patients must have  $\geq 3$  PSA measurements over  $\geq 3$  months
    - 2.1.1.3.7.2 The interval between PSA measurements must be  $\geq 4$  weeks
    - 2.1.1.3.7.3 For patients receiving 5-alpha reductase inhibitors (5ARI) e.g. finasteride or dutasteride, only PSA values obtained after at least 3 months on therapy may be used to calculate PSADT.
  - 2.1.1.3.8 Performance Status: ECOG 0-2 or Karnofsky 70-100%
  - 2.1.1.3.9 Life expectancy  $\geq 1$  year.
  - 2.1.1.3.10 Hemoglobin  $\geq 10.0$  gm/dL, WBC  $\geq 2,500/\text{mm}^3$ , ALC  $\geq 500/\text{mm}^3$ , ANC  $\geq 1,000/\text{mm}^3$ , platelet count  $\geq 100,000/\text{mm}^3$ .

- 2.1.1.3.11 PT/PTT  $\leq$  1.5X ULN unless receiving clinically indicated anticoagulant therapy.
- 2.1.1.3.12 SGOT/SGPT  $\leq$  2.5X ULN, total bilirubin  $\leq$  1.5X ULN, Cr  $\leq$  1.5X ULN, estimated GFR (eGFR)  $>$  60 ml/min.
- 2.1.1.4 Hepatitis B and C negative, unless the result is consistent with prior vaccination or prior infection with full recovery.
- 2.1.1.5 HIV negative
- 2.1.1.6 No use of investigational agents within 4 weeks of study enrollment.
- 2.1.1.7 No use of immunosuppressive (cytotoxic chemotherapy, systemic steroids) or immunomodulating agents (including IVIG) within 8 weeks of study entry. Note: topical and intranasal steroid therapy is permitted.
- 2.1.1.8 No other concurrent anticancer therapy.
- 2.1.1.9 No alternative medications known to alter PSA (e.g. phytoestrogens and saw palmetto). Note: patients receiving medications for urinary symptoms such as Flomax or 5-alpha reductase inhibitors (finasteride and dutasteride) on a chronic stable dose for at least 3 months are *allowed*.
- 2.1.1.10 No prior prostate cancer vaccines expressing TARP or HLA A2.
- 2.1.1.11 Able to understand and provide Informed Consent.
- 2.1.2 Exclusion Criteria
  - 2.1.2.1 HLA-A\*201 negative
  - 2.1.2.2 Patients with an active second malignancy other than adequately treated squamous or basal cell carcinoma of the skin, or superficial bladder carcinoma.
  - 2.1.2.3 Patients with active infection.
  - 2.1.2.4 Patients with brain, visceral or bony metastatic disease.
  - 2.1.2.5 Patients in who live attenuated intranasal influenza vaccine (FluMist™) is contraindicated including individuals with asthma or reactive airways disease, cardiovascular or pulmonary disease, chronic metabolic diseases (including diabetes mellitus), renal dysfunction or hemoglobinopathies.

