## **3 STUDY IMPLEMENTATION**

### **3.1 STUDY DESIGN**

This is a randomized, prospective pilot study of TARP peptide vaccination in HLA-A\*201 patients with Stage D0 prostate cancer. HLA-A\*201 positive eligible patients with *no evidence*

of brain, visceral or bony metastatic disease, a non-castrate testosterone level  $\geq 50$  ng/dL (prior ADT allowed; must be  $\geq 6$  months since last dose of ADT), and a PSADT  $> 3$  months and  $\leq 15$  months will be randomized to receive TARP peptides with Montanide® ISA 51 VG adjuvant plus GM-CSF administered by deep subcutaneous (SC) injection or autologous, TARP peptide-pulsed dendritic cells administered intradermally (ID).

TARP peptides or TARP-pulsed dendritic cells will be administered every three weeks at weeks 3, 6, 9, 12, and 15 for a total of five vaccinations with a booster dose of TARP vaccine given at Weeks 48 and 96. PSADT will be calculated in months at the following study time points: Pre-Enrollment/Baseline, weeks 12, 24, 36, 48, 60, 72, 84, 96, 108, 120, 132, and 144. PSADT will be calculated using the Memorial Sloan-Kettering Cancer Center cancer information prostate nomogram for PSA doubling time found at:

<http://www.mskcc.org/mskcc/shared/forms/Nomograms/flash/load.cfm?type=Prostate&width=586&height=505&title=Prostate%20Nomogram> as recommended in the Prostate Specific Antigen Working Group Guidelines. Cumulative PSA values within 12 months inclusive of the study time point will be used for calculation of the baseline/Week 0 PSADT.

Exploratory comparisons of percent change in PSADT will be done among the following time points:

[figure not shown]
- Pre-Enrollment/Baseline PSADT vs. Week 12 PSADT
- Pre-Enrollment/Baseline PSADT vs. Week 24 PSADT
- Pre-Enrollment/Baseline PSADT vs. Week 36 PSADT
- Pre-Enrollment/Baseline PSADT vs. Week 48 PSADT
- Week 24 PSADT vs. Week 36 PSADT
- Week 36 PSADT vs. Week 48 PSADT
- Additional exploratory analyses of PSADT will be performed of Pre-Enrollment/Baseline PSADT vs. Weeks 60, 72 and 96 and Week 48 PSADT vs. Weeks 96, 108 and 144 PSADT.

Week 24 PSADT responders will be allowed to receive an additional dose of TARP peptide vaccine at Week 36. All patients will receive a booster of vaccine at Weeks 48 and 96.

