### 5.2.2 PSADT Response Criteria

PSADT was chosen as a surrogate marker for biochemical response to vaccination based on the Prostate-Specific Antigen Working Group's consensus Guidelines on PSADT. Utilization of PSADT as a predictive factor of disease progression and prostate cancer death is based on level II evidence derived from cohort- or case-controlled analytic studies or controlled, non-randomized trials that have been validated in multiple data sets, PSADT will be calculated using the Memorial Sloan-Kettering Cancer Center cancer information prostate nomogram for PSA doubling time found at:

<http://www.mskcc.org/mskcc/shared/forms/Nomograms/flash/load.cfm?type=Prostate&width=586&height=505&title=Prostate%20Nomogram> recommended in the Prostate Specific Antigen Working Group Guidelines. The PSADT is calculated assuming an exponential increase in serum PSA and first order kinetics. The formula takes into account the natural logarithm of 2 divided by the slope obtained from fitting a linear regression of the natural log of PSA on time. All PSA values used in the calculation should be 0.20 ng/ml or greater and follow an increasing trend. PSA values need not be consecutively increasing and all values obtained during a maximum period of 12 months prior to a given protocol time point will be included in the calculation. The maximum period of the last 12 months is recommended to reflect current disease activity because in some men PSADT may change over time. Multiple studies concur that men with a PSADT < 3 months are at extremely high risk for metastatic disease progression

and death with prostate cancer mortality approaching 100%; for this reason they have been excluded from participation in this study. In contrast, men with a slow PSADT i.e. > 15 months have an extremely low risk of death from prostate cancer.

The following general guidelines regarding PSA determinations and calculation of PSADT used in this protocol will be adhered to (refer to [Appendix 5](#), PSADT Calculation Guidelines)

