#### **Pre-Enrollment/Baseline and On Study PSADT:**

- PSADT will be calculated using the Memorial Sloan-Kettering Cancer Center cancer information prostate nomogram for PSA doubling time found at:  
<http://www.mskcc.org/mskcc/shared/forms/Nomograms/flash/load.cfm?type=Prostate&width=586&height=505&title=Prostate%20Nomogram>
- Minimum requirements for PSADT include  $\geq 3$  PSA measurements over  $\geq 3$  months.
- The interval between PSA measurements must be  $\geq 4$  weeks.
- For patients receiving 5-alpha reductase inhibitors (5ARI) e.g. finasteride or dutasteride, only PSA values obtained after at least 3 months on therapy may be used to calculate PSADT.
- Calculated PSADT values will be reported in months
- The same laboratory must have performed PSA values used in the calculation of PSADT.
- All PSA values used in the calculation should be  $\geq 0.20$  ng/mL and follow a rising trend although all values need not be consecutively rising.
- All values obtained over a maximum period of 12 months prior to any given protocol time point assessment should be included in the PSADT calculation to reflect the patient's current disease activity.
- PSA values obtained within  $\leq 2$  weeks of instrumentation, documented infection (prostatitis), or radiation proctopathy should be *omitted* from inclusion in PSADT calculations.

On Study PSADT will be calculated at baseline and weeks 12, 24, 36, 48, 60, 72, 84, 96, 108, 120, 132, and 144.

Exploratory comparisons of percent change in PSADT will be done among the following time points:

- Pre-Enrollment/Baseline PSADT vs. Week 3-12 PSADT/
- Pre-Enrollment/Baseline PSADT vs. Week 24 PSADT
- Pre-Enrollment/Baseline PSADT vs. Week 36 PSADT
- Pre-Enrollment/Baseline PSADT vs. Week 48 PSADT
- Week 24 PSADT vs. Week 36 PSADT
- Week 36 PSADT vs. Week 48 PSADT
- Additional exploratory analyses of PSADT will be performed of Pre-Enrollment/Baseline PSADT vs. Weeks 60, 72 and 96 and Week 48 PSADT vs. Weeks 96, 108 and 144 PSADT.

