**Record PSA values with a maximum of 2 digits after the decimal point.**

On Study Sequential PSADT Calculated for Statistical Analysis			
Analysis Window	Study Wk PSA Values Included	Calculated PSADT/Slope Log	Percent Change PSADT
Pre-NIH	Outside PSAs -12 Months to Entry		
-12Months to Week 3	-12 Months plus Wks 0, 3		
Week 0 to Week 3	NIH PSAs only Wks 0, 3		
Week 3 to Week 12	Wks 3, 6, 9, 12		
Week 3 to Week 24	Wks 3, 6, 9, 12, 15, 18, 24		
Week 3 to Week 48	Wks 3, 6, 9, 12, 15, 18, 24, 36, 48		
Week 24 to Week 48	Wks 24, 36, 48		
Week 48 to Week 72	Wks 48, 60, 72		
Week 48 to Week 96	Wks 48, 60, 84, 72, 96		
Week 96 to Week 120	Wks 96, 108, 120		
Week 96 to Week 144	Wks 96, 108, 120, 144		

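### Baseline PSADT can include PSA values taken on ADT or during testosterone recovery, which can bias PSADT response and failure in either direction

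*Combined protocol and SAP*

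**What the plan says.** Prior ADT is compatible with entry. The précis, section 2.1.1.3.6 and section 3.1 agree: "prior ADT allowed; must be" at least 6 "months since last dose of ADT". Testosterone of at least 50 ng/dL is required for eligibility, but not at the date of each earlier PSA.

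Baseline PSADT uses a 12-month window. Section 3.1: "Cumulative PSA values within 12 months inclusive of the study time point will be used for calculation of the baseline/Week 0 PSADT". Section 5.2.2, for baseline and on-study values alike: "All values obtained over a maximum period of 12 months prior to any given protocol time point assessment should be included in the PSADT calculation". The Appendix 5B worksheet takes outside "PSAs -12 Months to Entry". The estimate is the "natural logarithm of 2 divided by the slope obtained from fitting a linear regression of the natural log of PSA on time".

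Some values are kept out. For men on 5-alpha reductase inhibitors, "only PSA values obtained after at least 3 months on therapy may be used to calculate PSADT". Values within 2 weeks of instrumentation, "documented infection (prostatitis), or radiation proctopathy should be *omitted* from inclusion in PSADT calculations". Values must be at least 0.20 ng/mL and rise overall, and baseline PSADT must lie above 3 and up to 15 months. No rule mentions ADT or testosterone recovery.

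Sections 1.1.1.1 and 6.1 describe the population as ADT-naive, which contradicts the eligibility text.

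**The concern.** A 6-month washout does not clear a 12-month window. For a man whose last ADT dose was 6 to 12 months before entry, following the rule as written mixes values taken on ADT, values during recovery and untreated growth in one regression line. The fitted slope is then not his untreated growth rate, and every comparison with baseline inherits the error.

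Baseline PSADT feeds four things:

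- the entry range in 2.1.1.3.7;
- the PSADT response and percent-change analyses in 5.2.2 and 6.2;
- the week 24 responder status that opens the week 36 dose;
- the PSADT failure and off-study rules in 5.2.2.1 and 3.6.3.4.

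With at most 20 men per arm, one misclassified man moves an arm's PSADT response rate by at least 1/20 = 5 percentage points.

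**Working it through.** The documents state no figure that depends on this point, so there is none to reproduce.

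**1. Overlap.** Window 12 months (3.1, 5.2.2) minus minimum washout 6 months (2.1.1.3.6) = up to 6 months of the baseline window on ADT.

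**2. Formula (5.2.2).** PSADT = ln 2 / b, where b is the least-squares slope of ln PSA on time.

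**3. Illustration A.** Assumptions, not in the documents: PSA on ADT is half its untreated level; last dose 6 months before entry; log-linear recovery complete at entry; evenly spaced, noise-free values; no vaccine effect. Let T be the true doubling time.

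- Slope over the 6 recovery months: ln 2/T + ln 2/6. For T = 12 this is 0.0578 + 0.1155 = 0.1733. For T = 24 it is 0.0289 + 0.1155 = 0.1444.
- Slope over the 6 months on ADT: ln 2/T if PSA grows in parallel at half level, or 0 if it is flat.
- The break is at mid-window, so the 12-month least-squares slope is the mean of the two segment slopes.

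| True PSADT | PSA on ADT | Fitted slope | Baseline PSADT (months) |
|---|---|---|---|
| 12 | parallel | (0.0578 + 0.1733)/2 = 0.1155 | 6.0 |
| 12 | flat | (0 + 0.1733)/2 = 0.0866 | 8.0 |
| 24 | parallel | (0.0289 + 0.1444)/2 = 0.0866 | 8.0 |
| 24 | flat | (0 + 0.1444)/2 = 0.0722 | 9.6 |

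A man with a true 24 months, outside the entry range, reads as inside it.

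**4. The same man on study (T = 12).** Week 24 is about 5.5 months, so its trailing 12-month window starts 6.5 months before entry and still holds the whole recovery. With PSA every 1 to 3 months before entry, and the scheduled visits afterwards, the fit gives 5.8 to 5.9: no response. By week 48 (about 11 months) the window holds essentially only values from entry on, and PSADT reads 12.0. Against baseline this is 12/6 = +100% or 12/8 = +50%. Both meet the response rule of a 50% or greater increase, the second exactly at the threshold.

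**5. Illustration B: earlier last dose.** Assumptions: T = 10; PSA flat on ADT; 3-fold rebound over 3 months; PSA every 1.5 months before entry.

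| Last dose before entry | Baseline | Week 24 | Week 36 |
|---|---|---|---|
| 6 months | 4.6 | 5.0 (no response) | 10.0 (false response) |
| 9 months | 4.0 | 10.0 (false response) | 10.0 |

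**6. Illustration C: no rebound.** PSA flat on ADT, last dose 6 months before entry, then growth at the true rate. For T = 6: (0 + 0.1155)/2 = 0.0578, so baseline reads 12.0. At week 24 it reads 6.0, a 50% decrease, which just meets the failure rule. For T = 10 and T = 14, baseline reads 20 and 28, above the 15-month limit.

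**7. Rebound needed.** PSA flat on ADT; T = 6, 10 or 14; recovery immediate or over 3 or 6 months. The second column is the rebound for an eventual false increase of 50% or more.

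| Last dose before entry | Rebound that shortens baseline | Rebound that gives a false response |
|---|---|---|
| 6 months | above 1.25 to 2.0-fold | 1.56 to 4.0-fold |
| 9 months | above 1.09 to 1.24-fold | 1.38 to 2.2-fold |

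**8. What an exclusion must cover.** In illustration B with the last dose at 6 months, all values give 4.6. Dropping only the values on ADT gives 3.9, which is worse. Dropping the recovery values too gives the true 10.

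**The case against.** The plan has partial safeguards. The 0.20 ng/mL floor removes deeply suppressed values, and the entry limit of more than 3 months removes most very large rebounds (10-fold in these illustrations). Testosterone must be non-castrate at eligibility. Only men with a last dose 6 to 12 months before entry have on-ADT values in the window. This stands as mitigation, but none of these rules excludes a moderate, rising recovery curve. The rising-trend rule does not either, because values need not rise consecutively.

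A reader might infer that the overlap always shortens baseline PSADT. Illustration C shows the reverse when there is no rebound, and the documents give no rebound size. The entry range does tilt the enrolled sample: it removes many lengthened baselines (20 and 28 are out) and keeps shortened ones above 3 months.

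A reader might also take the recovery slope alone and report 0.693/0.1733 = 4.0 months for a true 12, and 0.693/0.1444 = 4.8 for a true 24. The plan fits all values in up to 12 months, so these figures arise only if the values on ADT are absent or already dropped.

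Finally, a reader might infer that false responders generally gain the week 36 dose. Under the trailing window of 5.2.2 this does not happen in illustration A. It needs an earlier last dose, as in the second row of illustration B. The separate Appendix 5B window of weeks 3 to 24 holds on-study values only, so in both rows of illustration B it shows the false rise in the percent-change analysis.

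**Conclusion.** The gap is real. For men with recent ADT, the stated rule puts on-ADT or recovery values into the baseline slope. The direction depends on the rebound. With a rebound, baseline is too short and a false response can follow: 6.0 to 8.0 rising to 12.0 by week 48 in illustration A, or 4.0 rising to 10.0 at week 24 in the 9-month case. Without one, baseline is too long and a false failure can follow (12.0 falling to 6.0).

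The sizes rest on assumed, noise-free PSA paths. The documents give neither the number of affected men nor the size of any rebound, so the effect on the trial's PSADT response rate cannot be stated.

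The reach is limited to the secondary and exploratory PSADT analyses, the PSADT entry range, the extra-dose rule and the PSADT off-study rule. The primary immunologic endpoint and the two-stage sample size are not affected. The point should be corrected, but it does not threaten the trial's main conclusion.

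**What to change.** In section 5.2.2 and Appendix 5B, beside the 5-alpha reductase inhibitor line, add: *For the PSADT response and percent-change analyses, PSA values obtained on ADT, or before documented recovery to testosterone of at least 50 ng/dL, are not used, at baseline or on study.* The threshold is the plan's own. Also report the PSADT response rate with and without men who had ADT or recovery within the baseline window. That second analysis matters because PSA may still be rebounding after testosterone passes the threshold.

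Cost: a few men will have fewer than three usable values over 3 months and will not be evaluable for PSADT. Some outside PSA values will lack a paired testosterone, which the plan does not require.

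The sponsor should reconcile the ADT-naive wording in 1.1.1.1 and 6.1 with 2.1.1.3.6. It should also state whether the same restriction governs the PSADT used for eligibility, the extra dose and the off-study rule. That is not a one-line change. Excluding values from the first 6 months after the last dose, while still requiring three values over 3 months, would in effect move the minimum ADT-free interval to about 6 + 3 = 9 months. It would still not correct a slower recovery.

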## **2.2 RESEARCH ELIGIBILITY EVALUATION**

- 2.2.1 Protocol screening evaluation, other than the determination of HLA typing, will be performed within 2 weeks of study entry.
- 2.2.2 All patients will undergo a baseline history and physical examination including review of systems, performance status and life expectancy assessment. Radiologic evaluation (performed within 8 weeks of study) will include a, CT scan of the, chest, abdomen and pelvis, and a bone scan and may be performed at outside institutions. Laboratory studies will include a CBC with differential, platelet count, PT/PTT, chemistries (Acute Care Panel, Mineral Panel, Hepatic Panel, total protein, CK, Uric acid, LDH), PSA, testosterone, 25 hydroxy vitamin D, HIV-1 antibody, Hepatitis B Surface antigen (HBSAg) and antibody to Hepatitis B Surface antigen (anti-HBSag), Hepatitis C antibody (anti-HCV) and HTLV-1 antibody (anti-HTLV-1).
- 2.2.3 Refer to [Appendix 1](#) for the Schedule of Study Clinical, Laboratory and Radiographic Evaluations.

## **2.3 REGISTRATION PROCEDURES**

Authorized staff must register an eligible candidate with NCI Central Registration Office (CRO) within 24 hours of signing consent. A registration Eligibility Checklist from the web site (<http://home.ccr.cancer.gov/intra/eligibility/welcome.htm>) must be completed and faxed to [contact]. After confirmation of eligibility at Central Registration Office, CRO staff will call pharmacy to advise them of the acceptance of the patient on the protocol prior to the release of any investigational agents. Verification of Registration will be forwarded electronically via e-mail to the research team. A recorder is available during non-working hours.

### **Randomization Procedures**

Once registration is confirmed, enrolled patients will be randomized 1:1 to receive TARP peptides with Montanide® ISA 51 VG adjuvant plus GM-CSF administered by deep subcutaneous (SC) injection or autologous, TARP peptide-pulsed dendritic cells administered intradermally (ID):

Arm A (TARP peptides with Montanide® ISA 51 VG plus GM-CSF): study numbers 101-120

Arm B (TARP peptide pulsed dendritic cells): study numbers 201-220

All patients will undergo apheresis for immunologic monitoring. The apheresis will also be used for preparation of dendritic cells by elutriation of monocytes for dendritic cell culture, maturation and vaccine generation for those randomized to receive peptide-pulsed dendritic cells.

